11.1.6.4 Reporting of Pregnancy and Lactation to the Sponsor

Although pregnancy and lactation are not considered AEs, it is the responsibility of PIs or their designees to report any pregnancy or lactation in a subject (spontaneously reported to them) that occurs during the trial or within 14 days of completing the trial. All subjects or female partners of male subjects who become pregnant must be followed to the completion/termination of the pregnancy. Pregnancy outcomes must be reported.

Such events must be reported within 24 hours to the Sponsor either by electronic media or paper. Sponsor Contact information can be found in the Investigator Trial File Binder.

11.1.6.5 Serious Adverse Event

If any of the above AEs are serious (SAEs), as defined by the Food and Drug Administration (FDA) Code of Federal Regulations (CFR), Chapter 21, special procedures will be followed. All SAEs will be reported to the Sponsor within one working day and followed by written reports within five working days for non-expedited reports and three working days for expedited reports, whether or not the serious events are deemed drug-related. All serious event reporting will adhere to 21 CFR 312.32 for Investigational New Drugs (IND) and 21 CFR 314.80 for marketed drugs (15-day alerts). The institutional review board (IRB) will be notified by Celerion of the Alert Reports as per FDA regulations; FDA will be notified by the Sponsor or their designee.

SAEs will be followed until either the event is considered stable or resolved.

The following is the definition for a SAE as per FDA regulations:

A Serious Adverse Event (SAE) is any adverse drug experience occurring at any dose that results in any of the following outcomes: death, a life-threatening adverse drug experience, in-patient hospitalization, a persistent or significant disability/incapacity, or a congenital anomaly/birth defect. Important medical events that may or may not result in death, be life-threatening, or require hospitalization may be considered a serious adverse drug experience when, based upon appropriate medical judgment, they may jeopardize the patient or subject and may require medical or surgical intervention to prevent one of the outcomes listed in this definition.

If a SAE occurs to a subject on this study, contact the Sponsor's clinical representatives;								
PPD	Tel.: PPI	כ	E-mail:	PPD		and		
PPD	Tel:	PPD	E	-mail:	PPD			
listed in Section 2 and 3.								

12 DATA ANALYSIS

Data will be handled and processed according to Celerion Standard Operating Procedures, which are written based on the principles of Good Clinical Practices.

12.1 Pharmacokinetic Parameters

PK parameters for plasma total Mo will be calculated as follows:

AUC_{0-t}: The area under the plasma concentration versus time curve, from time 0 to the last measurable concentration, as calculated by the linear trapezoidal method. The area under the plasma concentration versus time curve from AUC_{0-inf}: time 0 to infinity. AUC_{0-inf} is calculated as the sum of AUC_{0-t} plus the ratio of the last measurable plasma concentration to the elimination rate constant. Maximum measured plasma concentration over the time span C_{max}: specified. t_{max}: Time of the maximum measured plasma concentration. If the maximum value occurs at more than one time point, t_{max} is defined as the first time point with this value. Apparent first-order terminal elimination rate constant calculated λz: from a semi-log plot of the plasma concentration versus time curve. The parameter will be calculated by linear least-squares regression analysis using the maximum number of points in the terminal log-linear phase (e.g., three or more non-zero plasma concentrations), beginning with the last non-zero concentration. Apparent first-order terminal elimination half-life will be calculated t_{1/2}: as 0.693/λz. CL/F Apparent oral clearance Vz/F Apparent oral volume of distribution

No value for λz , AUC_{0-inf}, $t_{\frac{1}{2}}$, CL/F, or Vz/F will be reported for cases that do not exhibit a terminal log-linear phase in the concentration versus time profile.

AUC and C_{max} parameters will not be calculated for subjects with only 2 or less timepoints with detectable concentrations.

12.2 Statistical Methods

Detailed methodology for summary and statistical analyses of the data collected in this trial will be documented in a Statistical Analysis Plan (SAP). The SAP will be prepared by

Celerion and agreed upon with the Sponsor. This SAP will not include any pharmacokinetic analysis. Additionally, a separate Pharmacokinetic Analysis Plan (PKAP) will be prepared by Kramer Consulting LLC and agreed upon with the Sponsor. This document may modify the plans outlined in the protocol; however, any major modifications of the primary endpoints definition and/or its analysis will also be reflected in a protocol amendment. Additional statistical analyses other than those described in this section may be performed if deemed appropriate and included in the SAP/PKAP.

12.2.1 Determination of Sample Size

The sample size chosen for this study was selected without statistical considerations. It has been determined adequate to meet the study objectives.

12.2.2 Descriptive Statistics

Arithmetic means, standard deviations (SD), sample size, coefficient of variation (CV), median, minimum and maximum values will be calculated for the plasma concentrations and the PK parameters listed in Section 12.1. Geometric means will be calculated only for AUC and C_{max} parameters.

12.2.3 Analysis of Variance

An analysis of variance (ANOVA) will be performed on the In-transformed AUC_{0-t} , AUC_{0-inf} and C_{max} . The ANOVA model will include sequence, treatment, and period as fixed effects, and subject nested within sequence as a random effect. Sequence will be tested using subject nested within sequence as the error term at a 10% level of significance. Each ANOVA will include calculation of geometric least-squares means (GLSM), the difference between treatment GLSM, and the standard error associated with this difference. The above statistical analyses will be done using SAS[®] PROC GLM.

12.2.4 Ratios and Confidence Intervals

Ratios of GLSM will be calculated using the exponentiation of the difference between treatment GLSM from the analyses on the In-transformed AUC_{0-t} , AUC_{0-inf} , and C_{max} . These ratios will be expressed as a percentage relative to the reference treatment.

Consistent with the two one-sided test for bioequivalence,⁹ 90% (Confidence Interval) CIs for the ratios will be derived by exponentiation of the CIs obtained for the difference between treatment GLSM resulting from the analyses on the In-transformed AUC_{0-t} , AUC_{0-inf} , and C_{max} . The CIs will be expressed as a percentage relative to the reference treatment.

The comparisons of interest are as follows:

- Treatment B compared with Treatment A
- Treatment A compared with Treatment C.

12.3 Safety Evaluation

All subjects who receive at least one dose of WTX101 will be included in the safety evaluation, and safety data will be populated in individual eCRFs. All safety data will be listed by subject.

Safety data including physical exams, ECGs, vital signs assessments, clinical laboratory evaluations, and AEs will be summarized by treatment group and point of time of collection, when applicable.

Descriptive statistics (arithmetic mean, SD, sample size, CV, median, minimum, maximum, and number) will be calculated for quantitative safety data as well as for the difference to baseline, when appropriate. In addition, a shift table describing out of normal range shifts will be provided for clinical laboratory results. A normal-abnormal shift table will also be presented for physical exam results and ECGs.

WTX101 and omeprazole dosing dates and times will be listed by subject.

AEs will be coded using the Medical Dictionary for Regulatory Activities (MedDRA[®]) Version 16.1 and summarized by treatment group for the number of subjects reporting the AE and the number of AEs reported. A by-subject AE data listing including (but not limited to) verbatim term, coded term, treatment group, severity, and relationship to treatment will be provided.

All concomitant medications recorded during the study will be listed by subject and coded with the WHO Dictionary Version 01Sep2013. Medical history will be listed by subject, and coded using the 16.1 version of MedDRA[®] dictionary.

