5 SYNOPSIS

Compound:	WTX101
Clinical Indication:	Wilson Disease (WD)
Study Phase and Type:	Phase 1 – Drug absorption and food-effect
Study Objectives:	 The primary objectives of the study are to evaluate: The effect of dosing with an Enteric coated (EC) tablet versus dosing with the current non-coated capsule administered with a proton pump inhibitor (PPI; omeprazole) under fasting conditions on the absorption of WTX101. The effect of dosing an EC tablet with and without food on the absorption of WTX101 The safety and tolerability of WTX101.
Summary of Study Design:	This will be a single-center, open-label, randomized, 3-period, 3-treatment, 6-sequence crossover study evaluating the absorption of WTX101 after single doses in healthy subjects based on the measurement of plasma total molybdenum (Mo). This study consists of a screening phase, three periods with similar procedures, and an end-of-study (EOS) visit. Screening of subjects will occur within 28 days prior to the first WTX101 dose.
	Subjects randomized to receive PPI in Period 1 (Treatment C) will report to the Clinical Research Unit (CRU) on Day -5, i.e. 5 days prior to first dosing with WTX101, to receive a morning dose of omeprazole under fasting conditions. These subjects will be given a container with omeprazole doses and will continue once daily (QD) administration of omeprazole under fasting conditions on an outpatient basis, until their return to the CRU for check-in on Day -1. To ensure that the planned number of subjects are dosed with WTX101 on Day 1 of Period 1, stand-by subjects will also receive QD doses of omeprazole, as described above. Should any subject withdraw from the study after omeprazole administration, but before receiving WTX101 in Period 1, they will be replaced with a stand-by subject.
	Subjects randomized to receive PPI in Periods 2 or 3 will receive the container with omeprazole doses prior to discharge from the CRU after the 192-hour post-dose procedures in Period 1 or Period 2, as appropriate. These subjects will initiate

	QD administration of omeprazole under fasting conditions at home the following day and continue until their return to the CRU for their next admission.

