Blinding:	This is an open-label study.	
Number of Subjects:	Eighteen (18) healthy, non-tobacco using adult male and female subjects between 19 and 55 years of age (inclusive).	
Dosage, Dosage Form, Route, and Dose Regimen:	WTX101 will be supplied as non-coated capsules or EC tablets for oral administration. Each WTX101 non-coated capsule (hydroxypropyl methylcellulose [HPMC]) contains 30 mg of bis- choline tetrathiomolybdate and the following excipients: anhydrous di-calcium phosphate and anhydrous sodium carbonate. Each WTX101 EC tablet contains 30 mg of bis- choline tetrathiomolybdate and the following excipients: tri- calcium phosphate, sodium carbonate, sodium starch glycolate, magnesium stearate. WTX101 EC Tablets are coated with Opadry 03K19229 Clear and Acryl-Eze White.	
	Dose regimens are described as follows:	
	Treatment A: 60 mg WTX101 (2 x WTX101 EC tablets, 30mg) at Hour 0 on Day 1 following an overnight fast.	
	Treatment B: 60 mg WTX101 (2 x WTX101 EC tablets, 30mg) at Hour 0 on Day 1, 30 minutes after the start of a high-fat breakfast, preceded by an overnight fast.	
	Treatment C: 20 mg omeprazole (1 x 20 mg delayed-release capsule) QD on the mornings of Days -5 to -1 following an overnight fast, 20 mg omeprazole capsule at Hour -1 on Day 1 following an overnight fast, and 60 mg WTX101 (2 x WTX101 non-coated capsules, 30mg) at Hour 0 on Day 1	
	All study medications (WTX101 non-coated capsules, WTX101 EC tablets and Omeprazole) should be administered orally with approximately 240 mL of room temperature water. The EC Tablets and non-coated capsules must be swallowed whole.	
Stopping Rules	Safety-related individual- and study-specific stopping criteria are detailed below:	
	Dosing will be discontinued for an individual subject experiencing any National Cancer Institute (NCI) Common Terminology Criteria for Adverse Events (CTCAE) version 4.0 (CTCAE v. 4.0) Grade 3 or higher event that is assessed as treatment-related.*	
	The study will be stopped if:	

	 2 or more subjects experience an NCI CTCAE v. 4.0 Grade 3 or higher event that is assessed as treatment-related*, or if 1 or more subjects experience a Grade 4 or higher event that is assessed as treatment-related*. *Treatment-related is defined as likely, probably, or possibly related per Section 11.1.6.3 of the protocol. 	

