9 STUDY OBJECTIVES, AND ENDPOINTS

9.1 Study Objectives

The primary objectives of the study are to evaluate:

- The effect of dosing with an EC tablet versus dosing with the current non-coated capsule coadministered with a proton pump inhibitor (PPI; omeprazole) under fasting conditions, on the absorption of WTX101.
- The effect of dosing an EC tablet with and without food on the absorption of WTX101.
- The safety and tolerability of WTX101.

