10 INVESTIGATIONAL PLAN

10.1 Overall Study Design and Plan

This will be a single-center, open-label, randomized, 3-period, 3-treatment, 6-sequence crossover study evaluating the PK of single doses of WTX101 in healthy subjects based on the measurement of plasma total Mo.

Please refer to the next page for the Study Diagram.

Figure 1 Study Diagram

Eighteen (18) healthy, non-tobacco using adult male and female subjects who complete the study screening assessments and meet all eligibility criteria will be enrolled. These subjects will receive the corresponding product, according to a randomization scheme generated at Celerion. To ensure that the planned number of subjects are dosed with WTX101 on Day 1 of Period 1, additional 'stand-by' subjects (who also complete the study screening assessments and meet all eligibility criteria) will also be enrolled. Subjects will be considered randomized when they receive the first dose of WTX101 on Day 1 of Period 1.

Subjects randomized to receive PPI in Period 1 (Treatment C) will report to the Clinical Research Unit (CRU) on Day -5, i.e. 5 days prior to first dosing with WTX101, to receive a morning dose of omeprazole under fasting conditions. These subjects will be given a container with omeprazole doses and continue QD administration of omeprazole under fasting conditions at home, until their return to the CRU for check-in on Day -1. To ensure that the planned number of subjects are dosed with WTX101 on Day 1 of Period 1, stand-by subjects will also receive QD doses of omeprazole, as described above. Should any subject withdraw from the study after omeprazole administration, but before receiving WTX101 in Period 1, they will be replaced with a stand-by subject.

Subjects randomized to receive PPI in Periods 2 or 3 will receive the container with omeprazole doses prior to discharge from the CRU after the 192-hour postdose procedures in Period 1 or Period 2, as appropriate. These subjects will initiate QD administration of omeprazole under fasting conditions at home the following day and continue until their return to the CRU for their next admission. For details on self-administration of omeprazole doses, see Section 10.5.1.

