10.5.2 Method of Randomizing Subjects to Treatment Groups

Each subject will be assigned a unique identification number upon screening. Subjects who complete the study screening assessments and meet all the eligibility criteria will receive the corresponding product, according to a randomization scheme generated at Celerion. To ensure that the planned number of subjects are dosed with WTX101 on Day 1 of Period 1, additional, stand-by subjects (who also complete the study screening assessments and meet all eligibility criteria) will also receive QD doses of omeprazole. Subjects will be considered randomized when they receive the first dose of WTX101 on Day 1 of Period 1.

Subjects will receive each treatment on one occasion. The sequences to be used in the randomization will be ABC, ACB, BAC, BCA, CAB, and CBA.

Subjects may be replaced at the discretion of the Sponsor.

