11.1.6.3 Reporting

AEs (including SAEs) will be recorded beginning with the first dose of study medication, either omeprazole or WTX101 (as per randomization), and through the EOS visit. AEs will be followed for 14 days after the last dosing with WTX101; or until the event resolves or stabilizes, whichever is earlier. All AEs that occur during this period will be recorded.

The PI will review each event and assess its relationship to drug treatment (likely, probably, possibly, unlikely or unrelated). Each sign or symptom reported will be graded on NCI CTCAE toxicity grading scale 5-point severity scale (Grade 1, 2, 3, 4 and 5).⁸

AE Severity	Definition
Grade 1	Mild; asymptomatic or mild symptoms; clinical or diagnostic observations only; intervention not indicated
Grade 2	Moderate; minimal, local or noninvasive intervention indicated; limiting age-appropriate instrumental ADL*
Grade 3	Severe or medically significant but not immediately life-threatening; hospitalization or prolongation of hospitalization indicated; disabling; limiting self-care ADL**
Grade 4	Life-threatening consequences; urgent intervention indicated
Grade 5	Death related to AE

The following definitions will be used for rating the severity of AEs:

Note 1: A semi-colon indicates 'or' within the description of the grade.

Note 2: Activities of Daily Living (ADL)

*Instrumental ADL refer to preparing meals, shopping for groceries or clothes, using the telephone, managing money, etc.

**Self-care ADL refer to bathing, dressing and undressing, feeding self, using the toilet, taking medications, and not bedridden.

The date of onset, time of onset, and outcome of each event will be noted. Additional variables to be recorded are as follows:

- Date and time when the AE started and stopped
- Maximum intensity
- Action taken
- Whether or not the AE is serious

- Whether or not the AE caused the subject to discontinue the study
- Outcome

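### Does basing the safety evaluation on a WTX101 dose lose subjects who take omeprazole in the Period 1 lead-in and never receive WTX101?

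*Protocol*

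**What the plan says.** Section 12.3 gives one inclusion rule for safety: "All subjects who receive at least one dose of WTX101 will be included in the safety evaluation". It then says that all safety data are listed by subject, that summaries are by treatment group, and that WTX101 and omeprazole dosing times are listed by subject.

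Other sections treat omeprazole as part of study treatment. The synopsis says "All study medications (WTX101 non-coated capsules, WTX101 EC tablets and Omeprazole) should be administered orally", and the drug belongs to Treatment C. Under Section 11.1.6.3, AEs are "recorded beginning with the first dose of study medication, either omeprazole or WTX101".

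The design also doses people who may never reach WTX101. The synopsis says "stand-by subjects will also receive QD doses of omeprazole, as described above", and Section 10.5.2 repeats this: "stand-by subjects (who also complete the study screening assessments and meet all eligibility criteria) will also receive QD doses of omeprazole". Section 10.1 covers early loss: should any subject "withdraw from the study after omeprazole administration, but before receiving WTX101 in Period 1, they will be replaced with a stand-by subject".

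Sections 10.1 and 10.5.2 count a subject as randomized at the first WTX101 dose on Day 1 of Period 1. The safety objective in Section 9.1 is "The safety and tolerability of WTX101".

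**The concern.** AE recording starts with omeprazole, but the safety evaluation starts with WTX101. The protocol itself creates people who fall between the two: lead-in withdrawals, and stand-by subjects who take omeprazole and are sent home unused. They are never counted as randomized, so they have no treatment group in summaries made by treatment group.

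If Section 12.3 were read as excluding everyone else, a subject who left the lead-in because of an AE would be absent from the safety tables. Such a subject is informative about tolerability. An AE in an unused stand-by subject could also be collected and then shown nowhere. Section 9.2 makes safety and tolerability a primary endpoint, so the gap deserves a check.

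**Working it through.** The protocol gives no figure to reproduce on this point, so the check compares passages. A short count then shows what can be said about size.

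**Who is affected.** Only the Period 1 lead-in matters. A subject who takes omeprazole before Period 2 or 3 has already received WTX101 in Period 1 and is inside the safety evaluation.

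**Does the set fit the question?** The objective (Section 9.1) names WTX101. Randomization is counted from the first WTX101 dose (Sections 10.1 and 10.5.2). A set defined by a WTX101 dose therefore contains the subjects counted as randomized, and it addresses the stated objective. Adding omeprazole-only subjects to the columns for A, B or C would be wrong, because they received none of those treatments in full.

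**Do Sections 11.1.6.3 and 12.3 contradict each other?** No. The first says when recording starts and the second says who is evaluated. In Treatment C omeprazole comes before WTX101, on Days -5 to -1 and again on Day 1. Recording has to start at omeprazole to capture lead-in AEs in subjects who later receive WTX101. A collection window wider than the analysis set is ordinary.

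**Where do the omeprazole-only data go?**

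- *Collection:* Section 11.1.6.2 monitors subjects during home omeprazole dosing, and requires AEs to be recorded in the eCRF whatever their relationship to drug and followed up.
- *Listings:* Section 12.3 lists all safety data by subject and states no restriction to the evaluated set.
- *Withdrawals:* Section 10.3.4 requires the clinical report to give reasons and relevant details. This reaches the most important case, a lead-in dropout because of an AE.
- *Serious events:* Section 11.1.6.5 requires every one to be reported to the sponsor, whether or not it is judged drug-related.

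**How many subjects?** Let *s* be the stand-by subjects given omeprazole and *w* the Treatment C starters who withdraw before WTX101. The protocol states neither. If stand-by subjects fill only the places of omeprazole starters and none of them withdraws, the number never receiving WTX101 is

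n = s + w − min(s, w) = max(s, w).

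For assumed values s = 2 and w = 2 this gives 2 + 2 − 2 = 2. Neither condition is fixed by the protocol:

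- If one of those two stand-by subjects also drops out, only one replacement is made and n = 2 + 1 = 3.
- Section 10.1 describes the purpose of stand-by subjects generally, as securing the planned number dosed on Day 1. If they may also fill Treatment A or B places, s = 2, w = 0 and two such vacancies give n = 0.

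So n is zero or more and cannot be derived from the protocol. For scale, 2 of the 6 sequences start with Treatment C. With equal allocation, which is an assumption, 18 × 2/6 = 6 planned subjects take omeprazole first, plus the stand-by subjects.

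**The case for a change.** The strongest case for a change is that Section 12.3 does not leave the matter open. It contains the only inclusion rule, that rule does not match the start of AE recording, and an SAP that copied it would inherit the mismatch. The line on listing all safety data follows the WTX101 rule and does not name omeprazole-only subjects. Even on a broad reading it gives listings and no summaries, and the AE listing carries a treatment-group field that is undefined for them. The withdrawal details in Section 10.3.4 do not reach an unused stand-by subject who has a non-serious AE. One sentence would settle all of this.

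Part of this stands. No passage says in terms where omeprazole-only subjects appear, and for unused stand-by subjects the listing line is the only support for reporting non-serious AEs.

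The rest does not carry a change. The rule says that WTX101-dosed subjects are included; it does not say that the listings stop there. A treatment-group field can simply read omeprazole only. Section 12.2 sends the detailed summary methods to an SAP that excludes pharmacokinetics, and the presentation of a few undosed subjects is routine content for it. Enlarging the safety set and then keeping the added subjects out of every treatment column would return the same A, B and C tables, with one extra column that might be empty.

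**Conclusion.** No change to the plan follows. The WTX101-dosed set is the correct basis for the by-treatment safety summaries, and followed as written it leaves the conclusion about WTX101 safety sound. What remains is a missing detail: whether subjects with omeprazole but no WTX101 appear in the listings. The natural reading of Section 12.3 is that they do, and analysts would list them separately as a matter of course.

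The group's size is unknown and may be zero. Safety is descriptive, and neither the pharmacokinetic comparisons nor the Treatment A, B and C columns depend on these subjects.

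This rests on two readings: that the statement on listing all safety data covers every subject with recorded safety data, and that the requirement for withdrawal details covers lead-in dropouts. If the listings were instead confined to WTX101-dosed subjects, the loss would be the listing of non-serious AEs in unused stand-by subjects, which bears on omeprazole and not on the stated objective.
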